4.1.3 Dosing Delays / Modifications

Treatment is administered according to the Time & Events Table (Section 5.6). Treatment will be delivered over 4-week cycles (1 cycle=28 days). Data will also be collected for patients that receive titrated dosing per investigator's discretion and following Table 1.

Toxicity will be evaluated using the NCI Common Terminology Criteria for Adverse Events, Version 4.0. The frequency of toxicities per organ system will be tabulated using descriptive statistics. All patients who receive any amount of the study drug will be evaluable for toxicity.

Subjects will be instructed to take 84,000 units (4 capsules) per main meal and 42,000 units (2 capsules) per snack. Should dose reductions be required per treating investigator, the following guidelines will be followed:

Table 1. Dose modifications

	Per meal	Per snack
Starting dose	84,000 USP units of	42,000 USP units of
	lipase (4 capsules)	lipase (2 capsules)
Dose modification 1	63,000 USP units of 21,000 USP unit	
	lipase (3 capsules)	lipase (1 capsule)
Dose modification 2	42,000 USP units of	21,000 USP units of
	lipase (2 capsules)	lipase (1 capsule)

Any dose modifications will be recorded in the research record, including dates. Compliance will be calculated based on the recommended dose.

4.1.4 Duration of Therapy

The patients will be followed on treatment for the 24-week study treatment period. Treatment may continue per SOC until death or until any of the following occur:

- Inter-current illness that prevents further administration of treatment
- Unacceptable adverse event(s)
- Patient decides to withdraw from the study, OR
- General or specific changes in the patient's condition render the patient unacceptable for further treatment in the judgment of the investigator.

In the absence of the above criteria, subjects may continue to receive study treatment at the investigator's discretion.

4.2 Concomitant Medications

Concurrent use of other pancreatic enzyme supplementation, fat-soluble vitamin supplements, or over the counter supplements which contain lipase, protease, and amylase as active ingredients is not permitted.

Only conmeds that are used to treat an adverse event deemed at least possibly related to Pancreaze need to be recorded in the REDCap database.

4.3 Duration of Follow-up

Patients will undergo an End of Study assessment 30 days after completion of the 24-week study treatment period. Patients removed from treatment for unacceptable adverse events will then be followed until resolution or stabilization of the adverse event and will continue to be followed for the duration of the study as per protocol. After the End of Study Assessment, follow-up will involve every 6-month phone calls to collect survival data for 36 months.

4.4 Removal of Patients from Protocol Therapy

Patients will be removed from therapy when any of the criteria listed in Section 5.7 apply.

4.5 Subject Replacement

Subjects who withdraw from the study treatment will be replaced.

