EOT End-of-Treatment FΑ Folinic Acid (Leucovorin) GLP-1 Glucagon-like peptide-1 H&P History & Physical Exam

HRPP Human Research Protections Program

IL1a Interleukin 1-alpha IV (or iv) Intravenously

MTD Maximum Tolerated Dose **LMF** Lipid Mobilizing Factors

LBM Lean Body Mass

NCI National Cancer Institute ORR Overall Response Rate

OS Overall Survival

PAWL Pancreatic Cancer-Associated Weight Loss

[figure not shown]
PBMCs Peripheral Blood Mononuclear Cells

PD Progression of Disease PFS Progression Free Survival

PR Partial Response

PYY Peptide YY

STUDY SCHEMA

Screening Phase

- 1. Informed consent
- 2. Screening
- 3. Eligibility review
- 4. Measure stool fecal elastase
- Measure fatsoluble vitamins

Treatment Phase

Cycle = 28 days

- 1. Measure weight stability
- 2. Assess 24-hour caloric intake
- 3. Assess stool frequency and consistency
- 4. Evaluate microbiome
- 5. Assess activity levels
- 6. Measure quality of life
- 7. Assess inflammatory biomarkers
- 8. Assess the presence of frailty phenotype
- 9. Assess body composition

End-of-Treatment

After C6D28:

- 1. Return pill bottles
- 2. Transition to Soc enzymes

Follow-up Phase

Safety evaluation

Measure fat-soluble vitamins

Survival

Optional sub-study: Followup activity tracking

STUDY SUMMARY

Title	Pancreatic-enzyme replacement therapy with pancreaze (pancrelipase) delayed-release in addition to standard of care for borderline resectable, locally advanced and advanced pancreatic adenocarcinoma patients (PANCAX-3) with cachexia and exocrine pancreatic insufficiency.		
Short Title	PANCAX-3		
Protocol Number	IIT2018-29-[name]-PNCX3		
Phase	Phase 2		
Methodology	Single arm, Single center		
Accrual Duration	18 months		
Study Duration	Approximately 6 months from screening to end of treatment assessment. Subjects will continue to be followed for survival for 36 months.		
Study Center(s)	Single-center, Cedars-Sinai Medical Center		
Objectives	 Feasibility to complete pancreatic enzyme replacement therapy at 8 weeks Measure weight stability at baseline and day 1 of every cycle for 6 months 24-hour caloric intake at baseline, C3D1, and end-of-study Stool frequency at baseline and C3D1 Quality of life assessment baseline and day 1 of every other cycle for 6 months Fitness tracking will be assessed with a wrist-worn wearable activity monitor (e.g., Fitbit Charge HR) continuously from day 1 of cycle 1 until the end of study visit. 		
Number of Subjects	Up to 40 patients (30 evaluable patients)		

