2.0 STUDY OBJECTIVES

2.1 Primary Objectives

2.1.1 Feasibility to complete pancreatic enzyme replacement therapy during the first 8 weeks of the study

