2.5 Endpoints

2.5.1 Primary endpoint

 Measure patient compliance to take pancreatic enzyme replacement therapy using a patient reported Pancreaze daily accountability log. Patient compliance will be defined as patients taking ≥ 50 % of the needed total lipase units. The primary endpoint will be met if at least 50% of the subjects in each cohort take at least 50% of the total needed lipase units within the first 8 weeks of treatment.

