2.5.2 Secondary endpoints

- Measure weight stability at baseline and day 1 of every cycle for 6 months
- Food intake will be assessed by study staff at C1D1, C3D1, and end-ofstudy. A validated 24-hour recall questionnaire will be analyzed using the automated self-administered 24-hour Dietary Assessment tool (ASA-24)
- Assess stool frequency at C1D1 and C3D1 using a stool survey
- Stool consistency at C1D1 and C3D1
- Measurement fat-soluble vitamins (including Vitamins A, D, E, and K) at baseline and end-of-study
- Evaluate microbiome at C1D1 and C3D1
- Activity (steps taken, stairs climbed, sleep duration and disturbances, heart rate and intensity) will be collected using the wearable activity monitor (e.g., Fitbit Charge HR) daily for the duration of the study.

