6.3.4 Evaluable for toxicity

Any patient who receives at least one dose of study drug is evaluable for toxicity and will be included in the safety analysis.

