9.0 STATISTICAL CONSIDERATIONS

9.1 Power Assessment

The primary hypothesis to be tested is whether the percentage of patients who complete the course of pancreatic enzyme replacement therapy at 8 weeks is at least 50% for each of the three cancer stage subgroups: borderline resectable, locally advanced and advanced pancreatic cancer. We assumed a sample size equal to 10 patients for each group. The minimum detectable difference from the proportion 0.5 is 0.417 using a Binomial Exact test with Bonferroni correction. Thus, we will declare the sustainability of the therapy if 9 or more patients complete the treatment for each subgroup.

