Amending Protocol v4 dated 13SEP2021 to Protocol v5 dated 17JAN2022

- Page 1, Abbreviations: Added abbreviation for End-of-Treatment (EOT)
- Page 2, Study Schema: Added EOT visit along with procedures. Clarified timing of fat-soluble vitamin measurements.
- Section 3.2, Exclusion Criteria: Removed exclusion criterion 3.2.7- other primary malignancies
- Section 5.3.3, Study Procedures: Addition of an EOT visit after C6D28, where patients will return
 pill bottles and transition to SoC enzymes, if applicable. The Day 15 visit was removed. The
 following study procedures will no longer occur at Day 15 of each cycle: PE, ECOG, and
 CMP/CBC
- Section 5.4, End-of-Study visit: Moved information pertaining to discontinuation of enzyme to section 5.3.3- End-of-Treatment visit.
- Section 5.6, Time and Events Table: Removed the Day 15 visit for each cycle and added an EOT visit. The footnotes were updated to reflect the changes to the study visits.

Amending Protocol v5 dated 17JAN2022 to Protocol v6 dated 14OCT2022

- Study Title: Updated the title to reflect that there are 3 cohorts for this study (resectable, locally advanced and advanced pancreatic adenocarcinoma).
- Sections 2.5.3, 5.1.16, 5.2 and 5.6: Removed the optional archival tissue sub-study.
- Section 6.2 Protocol-specific Adverse Event Monitoring Guidelines: Clarified that all serious adverse events regardless of expectedness or relatedness in addition to AESI need to be collected. Added a table of the expected toxicities for Pancreaze as indicated in the Package Insert.

Amending Protocol v6 dated 14OCT2022 to Protocol v7 dated 18MAY2023

- Update Co-Investigators to include [name]
 Increase sample size to 40 patients to allow for replacement of unevaluable patients.

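### Section 4.5 replaces patients who withdraw from treatment, but the plan does not say whether they stay in the denominator of the 8-week primary endpoint

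*Combined protocol and SAP*

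**What the plan says.** Section 4.5 is one sentence: "Subjects who withdraw from the study treatment will be replaced". It does not separate withdrawal before week 8 from withdrawal after it.

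The primary objective (Section 2.1) is "Feasibility to complete pancreatic enzyme replacement therapy during the first 8 weeks of the study". Section 2.5.1 calls the endpoint met if "at least 50% of the subjects in each cohort take at least 50% of the total needed lipase units" in that period. Section 9.1 assumes 10 patients per cohort and says "we will declare the sustainability of the therapy if 9 or more patients complete the treatment for each subgroup". Section 9.2 adds a 95% confidence interval for the completion proportion by stage.

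On numbers, the Study Summary gives "Up to 40 patients (30 evaluable patients"). The Appendix I entry for version 7 states the purpose of the larger number: "Increase sample size to 40 patients to allow for replacement of unevaluable patients".

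Evaluability is defined only for safety, in Section 6.3.4: "Any patient who receives at least one dose of study drug is evaluable for toxicity". Sections 2.5.1, 9.1 and 9.2 name no primary analysis set and do not say how a withdrawn or replaced patient is counted.

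**The concern.** A patient who stops before week 8 without reaching half of the needed units has failed the primary endpoint. If that patient is replaced and leaves the denominator, a failure is exchanged for a fresh chance of success, and both the rate and its interval move up. Section 5.7 lists inability to comply with the protocol among the reasons for discontinuation, so the event that may trigger replacement can overlap with the outcome being measured.

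If the patient stays in the denominator, the rate is sound, but the cohort may hold 11 or more patients while the cut-off was set for 10. Either way, the same data can give different rates, intervals and conclusions for the trial's only primary endpoint, depending on a choice that is not written down.

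**Working it through.** **Inputs from the documents.** Section 9.1: n = 10 per cohort, null proportion 0.5, three cohorts with Bonferroni correction, detectable difference 0.417, pass at nine or more. Study Summary: up to 40 enrolled for 30 evaluable, so at most 10 replacements (10/40 = 25%).

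**Assumptions.** The documents give no power, interval method, withdrawal rate or split of replacements by cohort. I take 80% power, exact (Clopper-Pearson) intervals, withdrawal rates over a range, and at most 3 replacements per cohort (10/3, rounded down).

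**1. The plan's own figure.** P(X ≥ 9 | n = 10, p = 0.5) = (10 + 1)/1024 = 0.0107, below 0.05/3 = 0.0167 one-sided. At p = 0.5 + 0.417 = 0.917, power = 10(0.917⁹)(0.083) + 0.917¹⁰ = 0.801. So 0.417 is reproduced, one-sided at 80% power.

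**2. One data set, two denominators.** Take 9 successes, 1 other failure and 2 early failures who were replaced.
- Dropped: 9/10 = 0.90, 95% CI 0.555 to 0.997.
- Kept: 9/12 = 0.75, 95% CI 0.428 to 0.945.

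The lower limit is above 0.5 in the first case and below it in the second.

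**3. If replaced early failures are dropped.** Let t be the true rate among all treated patients and w the share who are early failures and are replaced. The rate among those retained is q = t/(1 − w). With unlimited refilling, X ~ Bin(10, q). With the cap, a cohort closes at 10 retained or 13 enrolled, whichever comes first; the 50% rule is then applied to those retained.

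Section 9.1 rule (nine or more), t = 0.5:

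| w | q | Per-cohort pass, no cap | Per-cohort pass, at most 3 replaced |
|---|---|---|---|
| 0 | 0.500 | 0.011 | 0.011 |
| 0.10 | 0.556 | 0.025 | 0.024 |
| 0.20 | 0.625 | 0.064 | 0.050 |
| 0.25 | 0.667 | 0.104 | 0.066 |

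With the cap, the chance that all three cohorts pass is at most 0.066³ = 0.0003.

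Section 2.5.1 rule (at least 50% compliant), t = 0.4:

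| w | q | Per-cohort pass, no cap | Per-cohort pass, at most 3 replaced |
|---|---|---|---|
| 0 | 0.400 | 0.367 | 0.367 |
| 0.10 | 0.444 | 0.481 | 0.48 |
| 0.20 | 0.500 | 0.623 | 0.60 |
| 0.25 | 0.533 | 0.702 | 0.67 |

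**4. Who is replaced matters.** If only a fraction f of those replaced are failures, then at w = 0.25 and t = 0.5, q = (0.5 − 0.25(1 − f))/0.75. For f = 0.75, 0.5 and 1/3, q is 0.583, 0.500 and 0.444, and the uncapped chance of nine or more is 0.037, 0.011 and 0.004. The upward bias is gone at f = 0.5 and reverses below that.

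**5. If replaced patients are kept and the cut-off stays at nine.** P(X ≥ 9 | n, 0.5) is 0.033, 0.073 and 0.133 for n = 11, 12 and 13, all above 0.0167. At that one-sided level the cut-offs would be 10/11, 11/12 and 11/13.

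**The case against.** A reader might infer that the plan removes replaced patients from the primary analysis. It does not say so. Section 4.5 is an accrual rule in the treatment plan, not an analysis rule. The endpoint wording in 2.5.1 refers to the subjects in each cohort, which on its face keeps them, and Sections 4.3 and 5.5 continue follow-up after early removal or withdrawal. Unevaluable might mean never dosed (Section 10.3 lets registration be cancelled) or lacking a returned diary. Replacement might also serve the 6-month secondary endpoints, such as "Measure weight stability at baseline and day 1 of every cycle for 6 months". All of this stands: the defect is an undefined denominator, not a planned exclusion.

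Two further inferences go too far. One is that every withdrawal is replaced whatever its cause: Section 4.1.4 lists the patient's own decision to withdraw apart from adverse events and intercurrent illness, whereas 5.7 also uses the word for investigator decisions, so the scope is unclear. The other is that early stopping is the main way to fail. Low intake while still on treatment also fails, the documents give no split, and a fully adherent patient who stops after about week 4 has already taken about half of eight weeks' units.

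The 40-patient ceiling does reduce the larger uncapped figures, as the tables show. It does not change the direction, and neither reading of the denominator leaves the rule in 9.1 intact once a dosed early failure has been replaced.

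**Conclusion.** The gap is real and should be fixed. The plan replaces patients who withdraw but does not say how they count in its only primary endpoint, and both readings cause a problem.

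If early failures are dropped, each cohort's completion rate and interval are biased upward. With a true rate of 50% and 10% to 25% of patients being replaced early failures, the per-cohort chance of passing nine of 10 goes from 0.011 to between about 0.024 and 0.066, above the Bonferroni level of 0.0167. These are assumed rates, every replaced patient is taken to be a failure, and replacements are limited to three per cohort; the 25% case is an upper bound.

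A reader might infer a serious risk of a false overall claim under 9.1. The figures do not support that if all three cohorts must pass, since that chance stays below 0.001. The effect that matters is on the per-cohort rates and intervals, and on the 50% rule in 2.5.1, where a true rate of 40% passes a cohort with chance 0.37, rising to about 0.48, 0.60 and 0.67.

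The difference between the thresholds in 2.5.1 and 9.1, and the one-sided calculation set against the two-sided statement in 9.2, are separate points and are not argued here.

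**What to change.** Amend Sections 4.5, 2.5.1, 9.1 and 9.2 consistently:
- Define the primary set as the first 10 dosed patients in each cohort. This keeps the nine-of-10 rule intact, and replacements can still be enrolled for other endpoints.
- Count any of these 10 who stop before the end of week 8 below 50% of the needed units as non-compliant, even if replaced. Treat a stopper with no diary to show otherwise in the same way; diaries are returned at the end of each of the first two cycles, so a mid-cycle stopper may have none.
- Define evaluable for the primary endpoint and report the evaluable-only rate as a sensitivity analysis.
- If all dosed patients are preferred as the primary set, tie the cut-off to the actual n in each cohort.

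The cost is wording in four sections and no new data. The reported rate may be lower. Power for nine of 10 stays at 0.80 if 0.917 is the all-treated rate. If 0.917 was meant for non-withdrawers only, 5%, 10% or 20% early failures reduce the rate to 0.917 × 0.95 = 0.871, 0.917 × 0.90 = 0.825 or 0.917 × 0.80 = 0.734, and power to 0.62, 0.46 or 0.21. The plan should say which was meant.

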5.0 STUDY PROCEDURES

5.1 List of Study Procedures

5.1.1 Informed Consent – must be obtained within 6 weeks of Day 1

5.1.2 Review subject eligibility criteria

5.1.3 Pregnancy test

Pregnancy test for women of child-bearing potential as per standard of care.

5.1.4 Demographics

Age, gender, race, and ethnicity

5.1.5 Medical/surgical history

Complete medical and surgical history, history of infections

5.1.6 Physical exam including vital signs, height and weight

Vital signs (temperature, pulse, respirations, blood pressure), height (at screening/baseline only), weight

5.1.7 Performance status

Performance status evaluated prior to study entry according to Eastern Cooperative Oncology Group (ECOG) or Karnofsky performance status criteria (Appendix A)

5.1.8 Standard of care CT imaging

As indicated per standard of care, approximately every 8 weeks

5.1.9 Adverse event assessment

Signs/symptoms present at baseline prior to treatment initiation will be recorded as medical history. Adverse events will be assessed from time of treatment initiation for the duration of the study treatment period until the end-of-study visit. See Section 6 for Adverse Event monitoring and reporting.

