1.3 Rationale

Pancrelipase has been approved for the use in patients with exocrine pancreatic insufficiency due to cystic fibrosis or other conditions. In randomized studies it has improved fat absorption and decreased the stool frequency in these patients. However, its utility in advanced pancreatic cancer patients has not been evaluated to date.

Advanced pancreatic adenocarcinoma is characterized by progressive weight loss and nutritional deterioration [27]. It is estimated that up to 80% of these patients present with cachexia [28]. This wasting has been linked not only to survival, but also to alterations in host defenses, functional ability, and quality of life [29]. There have been few studies of whether nutritional support improves outcomes for these patients and the results have been inconsistent [30, 31]. This is despite evidence that artificial nutrition can improve performance status and other outcomes in terminal cancer patients [32].

Exocrine pancreatic insufficiency (EPI), which results from tumor-induced damage to the pancreatic parenchyma, obstruction of the pancreatic duct, and surgical removal of pancreatic tissue, is considered a major cause of this syndrome[33]. This deficiency impairs the body's ability to absorb fat, carbohydrates, and proteins, which results in steatorrhea, abdominal cramps, weight loss, and malnutrition[34]. Associated symptoms include foul-smelling flatulence, diarrhea, greasy stools, abdominal discomfort following meals, pain, bloating, and belching[34]. EPI is estimated to

affect 68% to 92% of patients with pancreatic cancer prior to surgery and as many as 94% of those following surgery[35].

There are few effective therapies for pancreatic cancer and none for its associated cachexia. Megesterol and Marinol are routinely prescribed for appetite stimulation but not effective[36]. Therapies attempting diet modifications and supplements have also failed to improve outcomes[37].

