One study randomized patients with pancreatic cancer to either 6 capsules of a high-dose pancreatic enzyme supplement per day or placebo for 8 weeks, with both groups receiving dietary counseling. Patients taking PERT gained 1.2% of their body weight compared with a 3.7% weight loss in the placebo group, with a mean difference in percentage of body weight change of 4.9% (P =.02; 95% confidence interval [CI] for the difference, 0.9%-8.9%). In addition, the fat absorption coefficient improved by 12% among those treated with PERT, while declining 8% for patients taking placebo (P =.13)[33].

Patients with borderline resectable, locally advanced, and advanced disease have distinct treatment paradigms and clinical outcomes. It is known that malabsorption is present in 68-92% of patients at diagnosis and most patients have associated symptoms [3, 6, 35, 38, 39]. In patients who had surgical resections, PERT was shown to improve the digestion of fat and associated symptoms of malabsorption [40]. As the cancer advances and the disease has spread to more area within the pancreas, the reliance on PERT is often increasingly recommended as the pancreas becomes less able to perform normal functions to aid in digestion of food. Previous studies have shown that lower trypsin, lipase and bicarbonate secretion are present in patients with non-resectable pancreatic cancer and pancreatic ductal obstruction [7]. As the utility of PERT varies with respect to each of the three cohorts of patients, it will be important to understand if there are some patient cohorts with an increased need for PERT.

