3.1 Inclusion Criteria

- **3.1.1** Borderline resectable, locally advanced, and advanced pancreatic cancer patients (can include new or recurrent diagnosis) referred to SOCCI-CSMC
- **3.1.2** Age ≥ 18 years.
- 3.1.3 ECOG performance status 0-1 or Karnofsky PS >60% (Appendix A)
- **3.1.4** Clinical diagnosis of exocrine pancreatic insufficiency
- 3.1.5 Cachexia defined as ≥5% weight loss in the presence of chronic illness, within any 6-month period prior to screening OR as documented by the medical physician based on standard diagnosis of cachexia
- **3.1.6** Life expectancy of greater than 3 months, in the opinion of the investigator.
- **3.1.7** Patients must have normal organ and marrow function as defined below:

Absolute Neutrophil Count (ANC)	≥500/mcL
Platelets	≥50,000/mcL
Total bilirubin	≤ 5X upper limit of normal (ULN)
AST(SGOT)/ALT(SGPT)	≤ 5 X ULN
Creatinine OR creatinine clearance	≤ 3 times the upper limit of normal OR ≥ 30 mL/min/1.73 m² for patients with creatinine levels above normal.

Note: Patients with biliary stents are eligible provided that all other inclusion criteria are met.

- **3.1.8** Woman of child-bearing potential (WOCBP) and men must agree to use adequate contraception (hormonal or barrier method of birth control; abstinence) from the time of signing the informed consent form, for the duration of study participation, and for at least 30 days after discontinuing from study treatment.
- **3.1.9** Ability to understand and the willingness to sign a written informed consent document

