5.2 Screening/Baseline Procedures

Assessments performed exclusively to determine eligibility for this study will be done only after obtaining informed consent. Assessments performed for clinical indications (not exclusively to determine study eligibility) may be used for baseline values even if the studies were done before informed consent was obtained.

All screening procedures used for eligibility verification must be performed within 4 weeks of Day 1 unless otherwise stated. Baseline procedures not required for eligibility verification can occur on Cycle 1, Day 1 of treatment (See section 5.3).

The screening and baseline procedures include:

- Informed consent
- Eligibility review, including:
 - Pregnancy test
- Demographics
- Medical/Surgical history
- Complete physical exam
- Standard of care CT imaging
- Height, weight, vital signs
- Performance status (ECOG or Karnofsky)
- AE (baseline symptom) assessment

- Concomitant medications review
- Labs: CBC/diff, CMP
- Blood draw for fat soluble vitamin levels
- Fecal elastase
 - Note: for maximum flexibility for the patients, the fecal elastase stool sample may be collected during screening or until C1D1 (+ 7 days).
 Patients will be encouraged to provide the fecal elastase stool sample prior to starting treatment, if possible.

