6.2 Protocol-specific Adverse Event Monitoring Guidelines

Since this supplement is FDA approved as part of standard of care in the patient population under study, only AEs of interest, as outlined below, will be collected and recorded in the EDC:

- Any event deemed serious and expected OR unexpected, regardless of cause.

 AND
- AEs of interest included below:

Expected toxicities to Pancreaze
Abdominal pain
Abdominal pain upper
Flatulence
Diarrhea
Abnormal feces
Fatigue

Note; All expected toxicities from chemotherapy can be found in the FDA approved Package Insert.

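### Five of the six non-serious adverse events of interest are symptoms of the entry disease, and the plan sets no reference grade and no rule for counting worsening from baseline

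*Combined protocol and SAP*

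**What the plan says.** Entry (section 3.1.4) requires a "Clinical diagnosis of exocrine pancreatic insufficiency". Section 1.3 describes that condition: "Associated symptoms include foul-smelling flatulence, diarrhea, greasy stools, abdominal discomfort following meals, pain, bloating, and belching". It adds that "malabsorption is present in 68-92% of patients at diagnosis and most patients have associated symptoms".

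Section 6.2 restricts safety data: "only AEs of interest, as outlined below, will be collected and recorded in the EDC". The list is all serious events, whatever their cause, plus six terms: abdominal pain, upper abdominal pain, flatulence, diarrhea, abnormal feces and fatigue.

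On baseline, section 5.1.9 says: "Signs/symptoms present at baseline prior to treatment initiation will be recorded as medical history". It continues: "Adverse events will be assessed from time of treatment initiation for the duration of the study treatment period until the end-of-study visit". Section 5.2 lists an "AE (baseline symptom) assessment" among the screening and baseline procedures, and the table in 5.6 marks adverse event assessment at screening. Section 5.3.1 places a CTCAE-graded safety evaluation on Day 1 of every cycle, which includes C1D1.

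The only stated analysis is in section 4.1.3: "The frequency of toxicities per organ system will be tabulated using descriptive statistics". That section cites CTCAE version 4.0, while 6.1, 6.4 and 6.6 cite version 5.

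**The concern.** Where the events of interest are also the symptoms of the disease being treated, a raw frequency means little unless it is tied to each patient's state before the first dose. The trial has one arm, so no comparator group shows how often these symptoms occur without Pancreaze.

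Two things are therefore needed: a reference grade for each term, and a rule that an event is a new symptom or one that has become worse than that grade. The plan states neither. A patient who enters with grade 1 diarrhea and reaches grade 3 on treatment could stay in medical history at one coordinator's hands and be entered as an event at another's, and neither would contradict an explicit instruction.

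The exploratory hypothesis in section 2.4.3 that supplementation is safe and tolerable is at stake, as far as it rests on non-serious events. A pre-dose grade that was not captured cannot be recovered at analysis.

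**Working it through.** The plan states no figure on this point, so there is none to reproduce. The check is a comparison of the text, followed by an illustration on assumed values.

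**Step 1: overlap of terms (6.2 against 1.3).**

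| Event of interest (6.2) | EPI symptom (1.3) |
|---|---|
| Abdominal pain | Pain; abdominal discomfort |
| Upper abdominal pain | Pain; abdominal discomfort |
| Flatulence | Flatulence |
| Diarrhea | Diarrhea |
| Abnormal feces | Greasy stools |
| Fatigue | Not listed |

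Five of six terms match (5/6 = 83%). Upper abdominal pain and abnormal feces match by meaning rather than by identical wording.

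**Step 2: is there a reference grade?** The screening assessment in 5.2 is not said to be graded. The C1D1 safety evaluation in 5.3.1 is graded, but it is not said to precede the first dose or to serve as the reference. Section 5.1.9 does not say whether a medical history entry carries a grade.

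**Step 3: is worsening an event?** The definition in 6.3.1 is broad but silent on a pre-existing condition that gets worse. Section 6.1 follows events until symptoms are back at their baseline level, which presupposes that the level is known. No section states the counting rule.

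**Step 4: how much could the rule matter?** The documents give no baseline prevalence for these terms, so the following values are assumptions. For one symptom, let b be the share of patients who have it at baseline, from 30% to 90%. Let w = 10% be the true rate of new onset among patients without it and of worsening among patients with it. The share tabulated is then:

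- any symptom on treatment counts: b + w(1 − b), if every baseline symptom persists
- only new onset counts: w(1 − b)
- new or worsened counts: w

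| b | Any on treatment | New onset only | New or worsened |
|---|---|---|---|
| 30% | 0.30 + 0.07 = 37% | 7% | 10% |
| 50% | 0.50 + 0.05 = 55% | 5% | 10% |
| 70% | 0.70 + 0.03 = 73% | 3% | 10% |
| 90% | 0.90 + 0.01 = 91% | 1% | 10% |

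The first column is an upper figure, because effective enzyme therapy would resolve some baseline symptoms. It is also the rule least compatible with 5.1.9. The more realistic contrast is between the last two columns. Their difference is bw, from 0.3 × 10% = 3 to 0.9 × 10% = 9 percentage points. That is 0.9 to 2.7 patients out of 30, or 1.2 to 3.6 out of 40.

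**Step 5: the denominator.** Section 6.3.4 puts everyone who received at least one dose in the safety analysis, and the Study Summary allows up to 40 patients with 30 evaluable. The safety denominator can therefore exceed 30.

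**The case against.** A reader might infer that baseline symptoms are ungraded. The documents do not say so. Sections 5.2 and 5.6 schedule a baseline symptom assessment, 5.3.1 schedules a graded evaluation at C1D1, and the case report forms are not part of the documents. Footnote 6 to the table in 5.6 has Pancreaze dispensed at C1D1, so that evaluation may well precede the first dose. Nor need the reference be as old as the 4-week screening window, because 5.2 allows baseline procedures not needed for eligibility on C1D1. This objection stands. What remains is that nothing requires the grade or makes it the reference.

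A reader might also infer that the table cannot separate worsening from disease. That is too strong. Events carry an onset date, a grade and an attribution (6.1, 6.6). Logging an unchanged baseline symptom as an event would conflict with 5.1.9. The broad definition in 6.3.1, read with the follow-up rule in 6.1, makes new-or-worsened the most natural reading. The stool survey at C1D1 and C3D1 and PROMIS-29 add data before and during treatment. In reply, attribution applies only once something has been logged, the natural reading is not written down, and neither instrument feeds the toxicity table.

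A reader might put a patient count on the problem: if 50% to 90% are symptomatic, 15 to 27 of 30. That prevalence is assumed, the statement in 1.3 about most patients does not refer to these five terms, and 30 is the evaluable number rather than the number dosed.

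Finally, safety is exploratory and descriptive, all serious events are collected, and the primary endpoint is adherence. This stands and limits the weight of the point.

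**Conclusion.** The concern holds in a limited form. Five of the six non-serious events collected are symptoms of the disease required for entry, pre-treatment symptoms go to medical history, and the stated analysis is a raw frequency. The plan does not require a pre-dose grade for these terms, does not designate a reference grade, and does not say that an increase in grade is an event. As specified, the toxicity table need not separate worsening on treatment from pre-existing disease.

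The number of patients affected is unknown. The figures in the working show only that a tabulated rate can depend on the unstated rule. They rest on assumed values of b and w, on the same w with and without baseline symptoms, and, for the highest figures, on baseline symptoms persisting.

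The primary endpoint is unaffected, so this is a minor change. It is worth making because it is cheap and the missing datum cannot be collected later.

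**What to change.** - **5.1.9, 5.3.1 and 5.6:** record the CTCAE grade of each of the six terms, with 0 for absent, at C1D1 before the first dose, within the safety evaluation already scheduled.
- **6.2 and 6.3.1:** define an event of interest as new onset or an increase over that grade.
- **4.1.3:** tabulate new-or-worsened events, with a shift table from baseline to worst grade for each term, in all patients who received at least one dose.
- **4.1.3 against 6.1, 6.4 and 6.6:** reconcile version 4.0 with version 5, so that baseline and on-treatment grades are on one scale.

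The cost is six data items per patient (6 × 30 = 180 to 6 × 40 = 240 entries) and one table, with no new visit or procedure. The change makes worsening from baseline countable. With one arm and concurrent chemotherapy, it does not show whether worsening is due to Pancreaze, chemotherapy or disease progression, and the report should say so.
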